3.0	
Synopsis: Updated for consistency with protocol
 
Schedule of Study Procedures and Evaluations:
 
 
Added “SARS-CoV-2 Serology Testing” to Visit 6 to determine if subject carries the antibodies
 
	15 June 2020

	

• Removed “X” from “Nasal Examination from Visit 3 and Visit 5”. Given the potential risks associated endoscopy and COVID-19 the frequency of these exams was reduced. Also, given the well-established safety profile of OPN-375, nasal examinations at the interim visits are not deemed necessary and efficacy measures are not required at interim timepoints.

• Removed “X” from “Nasal Polyp Grading from Visit 3 and Visit 5” and section 7.2 because nasal exams will not be required at these visits.

• Added abbreviation for “End of Study (EOS)” to be consistent in use of terminology

• Updated superscript comments to be consistent with protocol

 
Schedule of Study Procedures and Evaluations and Section 6.5:
 

• Added clarification to Visit 6 if subject cannot complete EOS CT scan at the Week 24 visit and continues treatment due to issues related to COVID-19 pandemic or due to any upper respiratory infection.

 
Section 1.3 Updated language to be more general and not specify countries
 
Section 3.1, 6.0 and 6.1
 

• Clarified timeline for CT completion at baseline.

 
Schedule of Study Procedures and Evaluations and Table 5;
 

• Removed “on site visit” and “office” to clarify urine pregnancy test must be completed at each visit

• Added a requirement for subjects who continue treatment past Week 24/Visit 6 to have an additional pregnancy test completed upon returning to site.

• Added “Blood Sample for SARS-CoV-2 serology testing” to Week 24/Visit 6 to determine if subject carries the antibodies

 
Synopsis and Section 4.1, (Inclusion Criterion 13)
 

• Removed “oral steroids” to address an inconsistency in protocol. Oral steroids are not allowed within 1 month of screening.

 
Synopsis and Section 4.2, (Exclusion Criteria 18)
 

• Revised to include “influenza, or SARS-CoV-2 (COVID-19)” to address new concerns related to COVID-19 pandemic.

 
Synopsis, Section 4.2, (Exclusion Criteria 34) and Section 5.6.3:
 

• Revised to include “cobicistat” to examples of cytochrome P450 3A4 inhibitors

 
Section 4.3
 

• Removed “receives systemic corticosteroids (oral or parenteral)” from reasons as subjects will no longer be withdrawn from the study per FDA request

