#### **4.3 Withdrawal and Removal of Subjects**

Subjects will be informed that they are free to withdraw from study treatment and/or the study at any time at their own request without prejudice to their future medical care, or that they may be withdrawn at any time at the discretion of the investigator or Sponsor for safety, nonadherence to protocol requirements, or administrative reasons (eg, termination of study by Sponsor). Subjects wishing to withdraw from study treatment will be strongly encouraged to continue in the study and have all scheduled study procedures performed.

A subject must be withdrawn from treatment for the following reasons:

- subject becomes pregnant
- A subject's study treatment will be discontinued if the investigator or Sponsor considers it in the subject's best interest to stop treatment, (eg, for safety or significant tolerability reasons such as an AE). Subjects who have one of the following AEs must be withdrawn from study treatment.
  - IOP of >21 mm Hg
  - nasal septal perforation
  - new onset or worsening of cataract

A subject may also be withdrawn from study treatment for the following reasons:

- lack of efficacy
- protocol violation

A subject may be withdrawn from the study for the following reasons:

- withdrawal of consent
- adverse event
- protocol violation that makes it unsafe for the subject to continue in the study
- termination of the study

- lost to follow up
- public health measure
- other

If a subject withdraws from the study after starting study treatment, appropriate follow-up must be conducted wherever possible.

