## 6 VISIT SCHEDULE SUMMARY

Procedures to be performed at each study visit, and the visit time windows, are indicated in the [Schedule of Study Procedures and Evaluations](#). Additional information related to the individual study visits is presented below:

- CT scans are required at Baseline and Week 24/ET to evaluate eligibility criteria and primary and secondary endpoints. All CT scans will be sent to a central imaging core lab for review and analysis. The baseline CT scan should be performed after all other screening assessments are completed for subjects who remain eligible (unless utilizing CT scan performed within 14-days prior to Visit 1).
- Subjects who develop an acute upper respiratory tract infection, acute sinusitis, influenza or SARS CoV-2 (COVID-19) during the study must be symptom free for at least 28 days prior to undergoing the Week 24/EOS CT scan. Subjects should continue treatment with study medication until EOS CT scan can be completed.
- For the Week 24 study visit, if the nasal examination or CT scan cannot be performed on the same day as the study visit, they should be performed *before the on site study visit*.

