AE=adverse event; CRF=case report form; DB=double-blind; EDS=Exhalation Delivery System; EOS=End of Study, ET=early termination; HPQ=Health and Work Performance Questionnaire; IWRS=interactive web response system; PGIC=Patient Global Impression of Change; EQ-5D=EuroQol-5; SF-36v2=36-Item Short Form Health Survey version 2; SNOT-22=Sinonasal Outcome Test – 22; PSQI = Pittsburgh Sleep Quality Index; QIDS = Quick Inventory of Depressive Symptomatology, SIT = Smell Identification Test.

**If subject cannot complete EOS CT scan at the Week 24 visit, subject should continue treatment until an EOS CT scan can be completed. If subject continues treatment:

- Complete Subject Contacts approximately every 4 weeks to assess safety until subject can complete the EOS CT scan
- When EOS CT scan has been completed and subject returns to study site, perform additional SNOT-22, and urine pregnancy test (women of childbearing potential only)

^a All visits up to Visit 6 (Week 24) should be scheduled based on the date of the Day 1 visit. If necessary, visits may be performed within the time window shown; however, subsequent visits should be scheduled based on the date of the Day 1 visit.

^b The assignment of a kit number for the demonstrator model EDS is not performed by IWRS, rather, the study staff will dispense a demonstrator model EDS kit and record the kit number in the drug dispensing log. This practice EDS is only used at the site at Visit 1 (Screening) and is not to be sent home with the subject.

^c Women of child-bearing potential only; urine pregnancy tests will be performed at each visit, not including subject contacts. Subjects continuing treatment past Week 24/Visit 6 will need an additional pregnancy test completed upon returning to site.

^d Nasoendoscopy will be performed using a rigid or flexible endoscope. The examiner must be able to visualize the middle meatus with the scope. Decongestants and/or local anesthetics may be used for the nasoendoscopic procedure.

^e The CT scan should be performed after diary eligibility is confirmed and prior to Day 21 of the screening run in period.

^f For the Week 24 study visit, the CT examination should be performed prior to the on-site visit.

^g Demonstrator model EDS kit (see footnote b) and single-blind placebo dispensation only.

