4.6 Considerations for statistical analysis resulting from the COVID-19 PHE

4.6.1 Co-Primary Endpoints

Since the co-primary efficacy variable CSNS is based on electronic diaries used by subjects during this study, as described in Section 9.3.1, there is no anticipated impact of COVID-19 on the subject's ability to complete the diaries per the protocol. Therefore, there is no anticipated impact of COVID-19 on this co-primary endpoint.

For the co-primary endpoint APOV, the endpoint CT scan will occur at the Week 24 visit, or the ET visit if the subjects discontinues the study prior to Week 24. Since subjects must visit the clinic for the CT scan, subjects may be impacted by COVID-19 in a manner similar to other acute illnesses as described in the Protocol, Amendment 6, Section 6. In this circumstance a subject must be symptom-free for at least 28 days prior to undergoing the Week 24/ET CT scan, and consequently the Week 24/ET visit may be delayed. Subjects are instructed to continue on treatment until the EOS CT scan can be completed. There is no anticipated impact of such a delay on the APOV co-primary endpoint.

Thus, there is no practical impact of the COVID-19 PHE on either of the co-primary endpoints.

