7.1.3 Primary Estimand

The primary efficacy estimand is the difference between each active treatment of twice-daily doses of 186 μg and 372 μg of OPN-375 and placebo for each of the co-primary endpoints.

For the primary estimand, intercurrent events will be addressed as follows:

1. Systemic corticosteroids use for CRS exacerbation or worsening of CRS nasal/sinus symptoms: a composite strategy will be employed with a poor score assigned to this event.

For CSNS, a value of '9' will be assigned; further detail regarding the assignment of a worst score to the diary data are provided in Section 9.3.1. For APOV, a poor score is defined as follows: for a subject with a baseline APOV $\geq 75\%$, a value of '100%' is assigned; if baseline APOV $< 75\%$, a poor score is defined as baseline APOV + 25%.

The rationale for assignment of a poor score is provided in Section [7.1.4](#) below. Further detail regarding the handling of a missing POV in individual sinuses is provided in Section [9.3.2](#).

Systemic corticosteroid use for other indications will be considered a treatment and study discontinuation event (reference criteria 3c).

2. Nasal surgery: composite strategy with poor scores assigned as above.
3. Treatment Discontinuation: treatment policy strategy; subjects may continue in the study until one of the following three mutually exclusive outcomes:
 - a) Subject completes Week 24/ET CT scan. In the absence of an intercurrent event (systemic corticosteroids, nasal surgery) use the endpoint value;
 - b) An intercurrent event (systemic corticosteroids for CRS exacerbation or worsening of CRS nasal/sinus symptoms, nasal surgery) occurs: use composite strategy and assign poor score as described above (reference criteria 1, 2);
 - c) Subject discontinues the study. Missing data due to study discontinuation following treatment discontinuation will be imputed; further detail on the imputation method is provided in Section [7.1.5](#) for each of the co-primary endpoints.

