7.3.2 Acute CRS Exacerbations – Pooled Analysis

How an acute CRS exacerbation is defined and captured in this study is described in Section 9.3.5. The frequency of acute sinus exacerbations over 24 weeks will be compared between OPN-375

dose groups and placebo using generalized linear model (GLM) for data from the negative binomial distribution that is commonly referred to as the negative binomial (NB) regression model. The NB model will include the same model terms as the primary models; in addition, the model will include a categorical effect for protocol (CS-3205, CS-3206), and the logarithm of exposure time as an offset variable.

Regarding intercurrent events, use of systemic corticosteroids is included in the definition of acute exacerbation; subjects who have surgery or study discontinuation events will be censored at the time of the intercurrent event. Subjects who discontinue treatment are followed to study completion or intercurrent event as described in Section 7.1.3.

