9.3.5 Acute CRS Exacerbations

An acute exacerbation of chronic rhinosinusitis event is defined as a worsening of symptoms requiring antibiotic or corticosteroid use, specifically:

- An acute worsening of one or more of the cardinal diagnostic symptoms of chronic rhinosinusitis (listed below), lasting at least 3 days, that causes the subject to seek medical care:
 - facial pain or pressure
 - nasal congestion/blockage
 - rhinorrhea
 - reduction in sense of smell

AND

- An escalation of treatment, defined as either initiation of treatment with antibiotics or systemic steroids, or the escalation of treatment involving an unscheduled acute care visit (e.g., emergency room or out subject clinic) or in-subject care, for increased symptoms related to sinusitis.

Date of onset of a CRS exacerbation event is defined by on the earliest onset date reported on the Exacerbation CRF; differentiation between CRS exacerbation events will also be determined from the onset dates reported on the Exacerbation CRF. If CRS exacerbation event start date is less than 7 days after the end date of a previous exacerbation, the entire period will be treated as a single exacerbation.

Duration of double blind period for each subject will be derived for this analysis as:

$$\text{Duration (days)} = (\text{Week 24/ET visit date} - \text{Date of Day 1}) + 1.$$

This duration of DB period will be the follow-up (exposure) time for analysis; subjects who did not experience any CRS exacerbation events during the DB period will be assigned '0' for frequency.

The time (weeks) to first acute CRS exacerbation event is defined as:

$$\frac{\text{start date of first CS exacerbation} - \text{date of randomization} + 1}{7}$$

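### Exacerbation rate: SAP 7.3.2 censors at surgery or study discontinuation, but the SAP 9.3.5 offset runs to the Week 24/ET visit; the expected effect is small and a wording change repairs it

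*SAP*

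**What the plan says.** SAP 7.3.2 compares exacerbation frequency over 24 weeks by negative binomial regression on pooled Studies 3205 and 3206, with log exposure time as offset. On intercurrent events it states that "subjects who have surgery or study discontinuation events will be censored at the time of the intercurrent event".

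SAP 9.3.5 derives, for each subject, a duration equal to the Week 24/ET visit date minus the Day 1 date plus 1, and adds: "This duration of DB period will be the follow-up (exposure) time for analysis". It mentions neither censoring nor a missing ET visit.

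Four other places decide how far apart the two end dates can be:

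- SAP 7.1.3: "Systemic corticosteroid use for other indications will be considered a treatment and study discontinuation event".
- Protocol 4.3 does not require such a subject to leave the study, and says: "Subjects wishing to withdraw from study treatment will be strongly encouraged to continue in the study". It also lists loss to follow-up as a reason for leaving.
- SAP 7.1.2 ties nasal surgery to study discontinuation, and Protocol 6.5 asks subjects who leave early to return for an ET visit.
- SAP 4.6.1 says of acute illness that "consequently the Week 24/ET visit may be delayed", because under Protocol 6 such subjects "must be symptom free for at least 28 days prior to undergoing the Week 24/EOS CT scan".

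**The concern.** In a count model, censoring is coherent only if the count and the offset stop on the same day. The same censoring sentence in SAP 7.5.10 causes no trouble, because in a Kaplan-Meier analysis the censoring date is itself the analysis time. In SAP 7.3.2 the time at risk is fixed elsewhere, by a formula that ignores censoring.

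Followed literally, an affected subject's rate is understated by the ratio of counted days to offset days. If more placebo subjects are affected, the rate ratio moves toward the null when the drug works. If more active subjects are affected, it moves away from the null. A subject without an ET visit has an undefined offset and would drop out of the fit. These are comparisons 3 and 4 of the alpha-controlled key secondary sequence (SAP 7.4.1), so the rule should not be left to programming judgement after unblinding.

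**Working it through.** **Plan's own figure.** The documents give no exacerbation rate, dispersion, censoring share or power for this endpoint, so there is nothing to reproduce for it. The co-primary power of 88% with 111 per group does reproduce (0.880 for CSNS, 0.877 for APOV) but has no bearing here. All shares and rates below are assumptions.

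**One subject.** Rate shown / true rate = counted days / offset days. With censoring on Day 56:

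- visit on Day 168: 56/168 = 33%
- ET visit 14 days after censoring: 56/70 = 80%

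**One arm.** Let p be the share censored, c the mean censoring time divided by 168, and g the days from censoring to the ET visit.

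- Offset to Day 168: factor = 1 - p(1 - c)
- Offset to ET visit: factor = [1 - p(1 - c)] / [1 - p(1 - c) + p·g/168]
- Rate-ratio multiplier = active factor / placebo factor

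Taking c = 0.5:

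| Placebo / active censored | Offset ends | Placebo factor | Active factor | Multiplier |
|---|---|---|---|---|
| equal shares | any | same | same | 1.000 |
| 5% / 2% | ET visit, g = 7 | 0.975/0.9771 = 0.9979 | 0.990/0.9908 = 0.9992 | 1.001 |
| 8% / 3% | ET visit, g = 28 | 0.960/0.9733 = 0.9863 | 0.985/0.990 = 0.9949 | 1.009 |
| 8% / 3% | Day 168, all censored | 0.960 | 0.985 | 1.026 |
| 3% / 8% | Day 168, all censored | 0.985 | 0.960 | 0.975 |

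The last two rows require every censored subject, not only those deemed discontinued, to have an offset run to Day 168. Under that same condition, harsher assumptions go further: 8%/3% with c = 0.25 gives 0.9775/0.94 = 1.040, and 15%/5% with c = 0.5 gives 0.975/0.925 = 1.054.

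**Type I error at the 8%/3% extreme.** The shift in z is ln(1.026)/SE = 0.0257/SE. For a log rate ratio SE of 0.15, 0.22 and 0.35, two-sided error is 5.34%, 5.16% and 5.06%.

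**Power at the same extreme.** Simulation used 500 runs per cell, dispersion 1.0, true ratio 0.6 and 111 to 222 per arm. With 8%/3% censored, the literal offset lowered rejection by 3.2 to 6.0 points. With 3%/8% it raised rejection by 2.4 to 4.8 points.

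**Missing ET visits.** A further simulation used a lag of up to 28 days, with 30% of affected subjects dropped at random for want of an ET date. Shares affected were 5%/5% or 10%/5%, with 111 or 185 per arm and true ratio 0.5. The estimated ratio moved by at most 0.005 and rejection by about 1 point.

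**Delayed scan.** Suppose the offset runs to the scan date while events are counted to Day 168, with placebo rate 0.2 to 0.6 per 24 weeks, true ratio 0.6 and episodes of 7 to 21 days. The simulated multiplier is 1.002 to 1.008. It is 1.000 if the true ratio is 1.

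**The case against.** The strongest reply is that SAP 7.3.2 is the endpoint-specific rule and SAP 9.3.5 only a general derivation. Censoring in a count model can have effect only by ending exposure, so a sensible programmer would truncate the offset. That reading is plausible, but the SAP does not state it. SAP 9.3.5 is written for this endpoint, covers each subject, and names its result as the exposure for analysis.

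Second, a subject given steroids for another indication may in fact leave. Protocol 4.3 allows withdrawal for nonadherence and has an open category, and Protocol 5.6.3 prohibits systemic steroids. It is also an inference that the study discontinuation events of SAP 7.3.2 include the deemed event of SAP 7.1.3. Both points stand in part: leaving is permitted but not required, so the long gap is possible rather than certain. The version history remark that "subjects will no longer be withdrawn from the study per FDA request" agrees with this, but the argument rests on the current Protocol 4.3.

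Third, a reader might infer that a late exacerbation materially lengthens the subject's own offset through the postponed scan. The documents do not support that. Protocol 6.5 has all other Week 24 procedures done on time, and the schedule includes the exacerbation assessment among them. What remains is an ambiguity: whether the Week 24 assessments, the scan, or completion of Visit 6 in the IWRS supplies the end date. The extra contacts ("Complete Subject Contacts approximately every 4 weeks to assess safety until subject can complete the EOS CT scan") name no exacerbation assessment.

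Finally, comparisons 3 and 4 are tested only after four co-primary and two key secondary comparisons succeed, which limits the stakes.

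**Conclusion.** The two sections conflict as written, and SAP 9.3.5 gives no end date for a subject without an ET visit. The defect should be corrected, but its expected effect is small: nil if affected subjects are balanced between arms, and a multiplier of about 1.001 to 1.009 where ET visits follow censoring by 7 to 28 days.

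A reader might infer serious bias or an inflated Type I error. The documents do not support either. The range 0.975 to 1.026, and the power shifts that go with it, need all censored subjects to have a Day 168 offset and also need unequal arms. Only steroid use for other indications is shown to permit that long gap, and nothing in the documents suggests it would differ by arm. Even then, Type I error stays between 5.06% and 5.34% over the standard errors tried.

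The conflict is certain on the text. Its size rests on assumed censoring shares, lags, event rates and dispersion, and on a Study 3206 analysis plan that is not among these documents.

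**What to change.** Before unblinding, amend SAP 9.3.5 as follows:

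- End follow-up at the earlier of the SAP 7.3.2 censoring date (including events deemed study discontinuation under SAP 7.1.3) and the Week 24/ET visit date. If there is no ET visit, use the last contact date in place of the visit date.
- Set follow-up to that date minus Day 1 plus 1, and count only exacerbations with onset in that same window.
- For a delayed end-of-study scan, state that the date of the Week 24 assessments (Protocol 6.5) ends both count and offset, not the later scan or IWRS completion date.

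The Study 3206 analysis should carry the same rule, because the data are pooled. The cost is wording only. Concomitant medications (Protocol 5.6) and the withdrawal date (Protocol 4.4) are already on the CRF, and concomitant procedures are in the visit schedule.

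An optional clarification while editing: SAP 7.3.2 takes its model terms from the two primary models, whose baseline covariates differ (CSNS and APOV). It could name the covariate intended, or say that there is none.

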7.4 Multiplicity - Type I Error Control

The study hypothesis encompasses the primary and key secondary endpoints; therefore, hypothesis tests for these endpoints are included in the strategy for strong control of the Type I error in the study. The familywise Type 1 error probability for the test of the primary hypothesis is $\alpha=0.05$, since the planned unblinded interim analysis of APOV endpoint did not occur (reference Section 4.5.1).

The strategy for strong, familywise control of the Type I error is based on closed testing procedure as follows.

1. Test each co-primary endpoint for OPN-375 high dose (372 μg) vs placebo: If
 - $p < 0.05$ for both endpoints, then proceed to test low dose comparison; otherwise, stop.
2. Test each co-primary endpoint for OPN-375 low dose (186 μg) vs placebo: If
 - $p < 0.05$ for both endpoints, then proceed to test key secondary endpoints; otherwise, stop.

There are two comparisons for each dose: OPN-375 high dose (372 μg) vs placebo and OPN-375 low dose (186 μg) vs placebo. The order of the testing is as follows:

1. OPN-375 372 μg versus placebo in the change from baseline in the 7-day average instantaneous AM CSNS at the end of Week 4
2. OPN-375 372 μg versus placebo in the APOV in the ethmoid and maxillary sinuses change from baseline to Week 24/ET
3. OPN-375 186 μg versus placebo in the change from baseline in the 7-day average instantaneous AM CSNS at the end of Week 4
4. OPN-375 186 μg versus placebo in the APOV in the ethmoid and maxillary sinuses change from baseline to Week 24/ET

